Grade 2 (except pneumonia - see Table 1-4)	If toxicity is tolerable to the patient, maintain the same dose. In case of intolerable toxicity for the patient, discontinue everolimus until recovery to grade ≤ 1 . Then reintroduce everolimus at the same dose. If an event returns to grade 2, discontinue everolimus until recovery to grade ≤ 1 . Then reintroduce everolimus at the lower dose level.
Grade 3 (except hyperlipidemia*) (except pneumonia - see Table 1-4)	Interrupt everolimus until recovery to grade ≤ 1 . Then reintroduce everolimus at the lower dose level. For pneumonia, consider short-term steroid therapy.
Grade 4	Stopping everolimus
Any non-hematologic toxicity requiring interruption for a period ≥ 3 weeks	Stopping everolimus

*Grade 3 hyperlipidemia (hypercholesterolemia and/or hypertriglyceridemia) should be managed with medical treatments.

Table 1-2

HEMATOLOGICAL Toxicity (NCI-CTC V4.0)	Grade	Actions
Thrombocytopenia	Grade 2 (platelets $< 75, \geq 50 \times 10^9 /l$)	Interrupt everolimus until recovery to grade ≤ 1 ($\geq 75 \times 10^9 /l$). Then reintroduce everolimus at the initial dose. If thrombocytopenia returns to grade 2, discontinue everolimus until recovery to grade ≤ 1 . Then reintroduce everolimus at the lower dose level.
	Grade 3 (platelets $< 50, \geq 25 \times 10^9 /l$)	Interrupt everolimus until recovery to grade ≤ 1 (platelets $\geq 75 \times 10^9 /l$). Then resume everolimus at a lower dose level.

		If thrombocytopenia recurs at grade 2, discontinue everolimus.
	Grade 4 (platelets < 25×10^9 /L)	Stopping everolimus
Neutropenia	Grade 3 (neutrophils < 1, $\geq 0.5 \times 10^9$ /L)	Interrupt everolimus until recovery to grade ≤ 1 (neutrophils $\geq 1.5 \times 10^9$ /L). Then resume everolimus at the initial dose. If PNN returns to grade 3, withhold everolimus until PNN is $\geq 1.5 \times 10^9$ /L. Then resume everolimus at the lower dose level. Discontinue study treatment if a third episode of Grade 3 neutropenia occurs
	Grade 4 (neutrophils < 0.5×10^9 /L)	Interrupt everolimus until recovery to grade ≤ 1 (neutrophils $\geq 1.5 \times 10^9$ /L). Then resume everolimus at the lower dose level. If Grade 3 or 4 neutropenia occurs despite this dose reduction, discontinue everolimus

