Febrile neutropenia	Grade 3	Discontinue everolimus until fever resolves and grade ≤ 1 neutropenia returns. Continue everolimus interruption until PNN is $\geq 1,500/\text{mm}^3$ and fever disappears. Then resume everolimus at the lower dose level. If febrile neutropenia recurs, discontinue everolimus.
	Grade 4 (life-threatening)	Stopping everolimus
Any hematological toxicity	Requiring an interruption for a period ≥ 3 weeks	Stopping everolimus

Table1-3:

Toxicity ANEMIA (Hemoglobin decrease) NCI-CTC v4.0	Grade	Dose adjustment
Anemia	Grade 1 or 2	No change in dose
	Grade 3	Interrupt everolimus until recovery to grade ≤ 2 , then resume everolimus at the same dose. If return to grade 3, withhold everolimus until grade ≤ 2 , then resume at lower dose level. Discontinue everolimus in case of 3 ^{ième} grade 3 episode.
	Grade 4	Permanent discontinuation of everolimus

b. Known adverse reactions to everolimus

-The most common grade -34 adverse events -(frequency $\geq 2\%$ in at least one pivotal study) were anemia, fatigue, diarrhea, infections, stomatitis, hyperglycemia, thrombocytopenia, lymphopenia, neutropenia, hypophosphatemia, hypercholesterolemia, diabetes mellitus, and pneumonitis. Grades follow the CTCAE version 4.0 classification.

Everolimus has immunosuppressive properties and may predispose patients to bacterial, fungal, viral or protozoal infections, including infections with opportunistic pathogens. Localized and systemic infections, including pneumonia, other bacterial infections, invasive fungal infections such as aspergillosis or candidiasis, and viral infections, including cases of hepatitis B reactivation, have been described in patients treated with everolimus. Some of these infections have been severe (e.g., leading to respiratory or hepatic failure), sometimes with fatal outcome.

Physicians and patients should be aware of the increased risk of infection with everolimus. Pre-existing infections should be treated before starting everolimus therapy. During treatment with everolimus, vigilance for signs and symptoms of infection should be exercised; if an infection is diagnosed, appropriate treatment should be initiated as soon as possible and temporary or permanent discontinuation of everolimus should be considered. If a diagnosis of invasive systemic fungal infection is made, everolimus must be discontinued and appropriate antifungal therapy initiated.

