2. For more severe toxicity (grade 2, in which case patients are able, despite pain, to maintain adequate oral nutrition, or grade 3 in which case patients cannot maintain adequate oral nutrition), the proposed treatments are **analgesic topical oral treatments (i.e., local anesthetics such as benzocaine, butylaminobenzoate, tetracaine hydrochloride, menthol, or phenol)** with or without **topical corticosteroids**, such as triamcinolone acetonide 0.1% gingival paste (Orabase Kenalog®).
3. Agents containing hydrogen peroxide, iodine and thyme derivatives may tend to exacerbate mouth ulcers. It is best to avoid these agents.
4. Antifungal agents should be avoided unless a fungal infection has been diagnosed. In particular, systemic imidazole antifungal agents (ketoconazole, fluconazole, itraconazole, etc.) should be avoided in all patients as they are potent inhibitors of everolimus metabolism, resulting in higher everolimus exposures. Therefore, topical antifungal agents are preferable if an infection is diagnosed. Similarly, antiviral agents such as acyclovir should be avoided unless a viral infection is diagnosed.

d. Management of hyperlipidemia and hyperglycemia

Hyperlipidemia and hypertriglyceridemia should be treated according to local best clinical practice.

e. Management of non-infectious lung disease

Non-infectious pneumonitis is a class effect of rapamycin derivatives. Non-infectious lung disease (including interstitial lung disease) has also been described in patients treated with everolimus. A diagnosis of non-infectious lung disease should be considered in patients presenting with non-specific respiratory signs and symptoms such as cough or dyspnoea, hypoxia, pleural effusion, and when infectious, neoplastic or other non-drug causes have been excluded by appropriate investigations. Patients should be asked to report promptly any new or worsening respiratory symptoms.

Patients with radiological changes suggestive of non-infectious lung disease with few or no symptoms may continue everolimus therapy without a change in dosage. In the presence of moderate symptoms (Grade 2), discontinuation of treatment should be considered until symptoms improve. Administration of corticosteroids may be indicated. Everolimus may be reintroduced at a reduced dose until recovery to Grade 1 or higher.

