When symptoms of non-infectious lung disease are severe (Grade 3), everolimus treatment should be discontinued and corticosteroids may be indicated until clinical symptoms resolve. Everolimus treatment may be reintroduced at a reduced dose depending on individual clinical circumstances.

Table 1-4Management of non-infectious lung disease

PNEUMOPATHY (NCI-CT V 4.0)	INVESTIGATION REQUIRED	CARE	EVEROLIMUS DOSE ADJUSTMENT
Grade 1	Chest CT in the lung window and respiratory function tests, including spirometry, DLCO, and room air O ₂ saturation at rest. Repeat chest x-ray/computed tomography every 2 cycles until normal.	No specific treatment is required	Administer 100% of the everolimus dose.
Grade 2	Chest CT in lung windows and pulmonary function tests, including spirometry, DLCO, and room air O ₂ saturation at rest. Repeat with each subsequent cycle until normalcy is achieved.	Symptomatic only. Prescribe corticosteroids if cough is troublesome.	Reduce everolimus dose until recovery to a grade \leq 1. Everolimus may also be discontinued if troublesome symptoms occur. Patients will discontinue treatment if they fail to recover to a grade \leq 1 within 3 weeks
Grade 3	Bronchoscopy is recommended *	Prescribe corticosteroids if an infectious origin is excluded. Gradually reduce the dose according to medical indication.	Withhold treatment until recovery to a grade \leq 1. The treatment protocol may be restarted within 2 weeks at a reduced dose (by one level) if there is evidence of clinical benefit. Patients will discontinue treatment if they fail to recover to a grade \leq 1 within 2 weeks.
Grade 4		Prescribe corticosteroids if an infectious origin is excluded. Gradually reduce the dose according to medical indication.	Stop the treatment.

*Bronchoscopy with biopsy and/or bronchoalveolar lavage is recommended.

f. Management of reactivation /flare-up of hepatitis

In cancer patients with hepatitis B virus, either carrier or chronic, the administration of antivirals during cancer therapy has been shown to reduce the risk of hepatitis B virus (HBV) reactivation and associated morbidity and mortality (Loomba et al. 2008).

- **Monitoring and prophylaxis for hepatitis B reactivation**

Table 2-1 provides detailed information on monitoring and prophylactic treatment based on initial viral load and serologic marker test results.

Table 2-1: Actions to be Taken for Initial Positive Hepatitis B Results

Test	Result	Result	Result	Result	Result
HBV DNA	+	+ or -.	-	-	-

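### The grade 3 row of Table 1-1 excepts pneumonia and then gives it a steroid instruction, without the condition on infection that Table 1-4 states

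*Protocol*

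**What the plan says.** **Table 1-1 (Protocol VII.2.a)** covers toxicities that are neither hematological nor hepatic. The grade 2 row is labelled "Grade 2 (except pneumonia - see Table 1-4" and the grade 3 row carries "except hyperlipidemia*) (except pneumonia - see Table 1-4", so both rows hand the event to Table 1-4. The grade 3 action cell interrupts everolimus until grade 1 or lower, restarts it one dose level down, and then adds "For pneumonia, consider short-term steroid therapy". The last row stops everolimus for any non-hematological toxicity that needs an interruption of 3 weeks or more. It makes no exception for lung events.

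**Table 1-4 (Protocol VII.2.e)** has the title "Management of non-infectious lung disease", and its first column is headed "PNEUMOPATHY (NCI-CT V 4.0". For grades 3 and 4 the care column says "Prescribe corticosteroids if an infectious origin is excluded". For grade 2 it says "Prescribe corticosteroids if cough is troublesome". At grade 3, treatment ends if the patient has not recovered to grade 1 or lower within 2 weeks. The prose of VII.2.e treats non-infectious lung disease as a diagnosis of exclusion, with infection among the causes to be ruled out first.

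**Section VII.2.b** describes what has been seen under everolimus: "Localized and systemic infections, including pneumonia, other bacterial infections, invasive fungal infections such as aspergillosis or candidiasis". It names pneumonitis separately, among the common grade 3-4 events. For a diagnosed infection it asks for prompt treatment and for temporary or permanent discontinuation of everolimus to be considered.

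**The concern.** A row that excludes an event should not also instruct on it. Here the instruction is about steroids, and what it lacks is the condition on infection that the referenced table states at the same grade. The protocol itself describes everolimus as immunosuppressive and reports that some infections under it were fatal. Section VII.2 points sites to Tables 1.1 and 1.2 for dose adjustment, so Table 1-1 is where a site will look first. Two sites could handle the same lung event differently, both on steroids and on when everolimus is stopped for good.

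**Working it through.** No arithmetic underlies the point beyond one difference in time limits. The check sets the texts side by side.

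1. **The row against itself.** The grade 3 label excludes pneumonia and the grade 3 action cell addresses it. Both cannot be operative. This does not depend on what pneumonia means.

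2. **The steroid wording.**

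| Place | Steroid wording | Condition on infection |
|---|---|---|
| Table 1-1, grade 3 | to be considered, short term | none |
| Table 1-4, grade 2 | if cough is troublesome | none in the cell |
| Table 1-4, grades 3 and 4 | to be prescribed | infectious origin excluded |
| VII.2.e prose, grades 2 and 3 | may be indicated | through the diagnosis, which requires infection to be ruled out |

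At grade 3, Table 1-1 lacks a condition that Table 1-4 states. That is an omission, not an opposite instruction. The grade 2 cell of Table 1-4 also lacks the condition, so the inconsistency is not confined to Table 1-1.

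3. **The term, under two readings.**
   - *Pneumonia in Table 1-1 means the non-infectious disease of Table 1-4.* The cross-reference then works and infection should already have been ruled out at diagnosis. The self-contradiction in step 1 remains, and there are still two steroid statements for one event.
   - *Pneumonia means an infection, as in VII.2.b.* The cross-reference then leads to a table whose title excludes the event, and the steroid sentence has no safeguard beside it.

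   The documents do not say which reading is meant.

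4. **The time limit at grade 3.** Table 1-1 stops everolimus for an interruption of 3 weeks or more (21 days). Table 1-4 stops it without recovery within 2 weeks (14 days). The difference is 21 - 14 = 7 days. A patient who recovers to grade 1 or lower after day 14 but before day 21 may restart under Table 1-1 and is stopped under Table 1-4. Table 1-4 also ties restart to evidence of clinical benefit, which Table 1-1 does not. At grade 2, Table 1-4 also uses 3 weeks, so the two limits agree there.

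5. **Reach into the analysis.** SAP 5.7.1 defines the primary endpoint as being alive without liver progression 24 months after inclusion. Stopping everolimus is not part of it. What depends on these rules is the descriptive reporting of dose changes, temporary stops and permanent discontinuation under SAP 7.6.2.

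**The case against.** The strongest reply is that Table 1-1 must be read with the rest of section VII.2. Its cross-reference leads to a table whose title limits it to non-infectious disease. VII.2.e requires infection to be ruled out first, and VII.2.b deals with diagnosed infection. The protocol also reads as a translation, with French remnants in its table of contents, and VII.2.e uses several terms for one entity. Pneumonia in Table 1-1 may simply stand for the pneumopathy of Table 1-4. If so, the missing condition is redundant, because infection has already been excluded.

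Much of this stands, and it rules out three stronger conclusions that a reader might draw:

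- *That infectious pneumonia is misrouted and left without guidance.* VII.2.b covers diagnosed infection. Misrouting follows only from a literal reading of one word.
- *That referral to Table 1-4 loses the interruption rule.* Table 1-4 at grade 3 also withholds everolimus until grade 1 or lower. Table 1-1 at grade 2 has no default interruption: it keeps the dose if the toxicity is tolerable, whereas Table 1-4 reduces it.
- *That a given number of the 72 patients is affected.* The documents state no frequency of pneumonia in this population, and a count of pneumonias would not be a count of misapplied rules.

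The reply does not remove the self-contradiction in the grade 3 row, the unmatched terms, or the two time limits. VII.2.b gives no grade-based rule and no steroid rule, and the step of excluding infection does not sit beside the instruction in Table 1-1.

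**Conclusion.** The point holds as an unresolved contradiction in an operative safety table. The grade 3 row of Table 1-1 both excepts pneumonia and instructs on it, its steroid sentence omits a condition that Table 1-4 states at the same grade, and the limit for permanent discontinuation at grade 3 differs by one week between the tables. Application of the non-infectious table or of unconditional steroids to an infectious pneumonia is a possible consequence of a literal reading, not an established one.

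The size in patients cannot be given from the documents. There is no effect on sample size, alpha, power or the primary analysis; any effect on the results is limited to descriptive tolerance tables. The conclusion rests on the wording alone and does not depend on whether pneumonia is a translation of pneumopathy. The point should be addressed, because the text concerns an immunosuppressive drug and the correction is small.

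**What to change.** Reconcile Tables 1-1 and 1-4 with sections VII.2.b and VII.2.e:

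- Use one term for the same event in both tables, including both exception notes in Table 1-1.
- Reword the grade 3 row of Table 1-1 so that it does not both except the event and instruct on it.
- Keep a single steroid rule in one place, with its condition on infection stated consistently, and check the grade 2 cell of Table 1-4 against it. Section VI.3 lists corticosteroids with the potent inducers whose concomitant use is to be avoided, so that text belongs in the same check.
- State which interruption limit applies to a grade 3 lung event.
- State which rule applies to infectious pneumonia.

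The sponsor's clinicians decide the content of each rule; this review takes no view on it. The cost is a wording change in a protocol amendment or a memo to sites, with no change to data collection, sample size or analysis.

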syndrome, somatostatin analogue therapy is not permitted after embolization or chemoembolization.

VII. EXPECTED TOXICITIES AND DOSE ADJUSTMENT

1. Dose adjustment after the first embolization or chemoembolization

No dose adjustment of doxorubicin or streptozotocin is planned for chemoembolization sessions. There are no plans to adjust the dose of lipiodol for embolization sessions.

Embolization or chemoembolization will only be performed if hematological, renal and hepatic functions are satisfactory i.e. if:

- PNN $\geq 1.5 \times 10^9$ /L,
- Platelets $\geq 75 \times 10^9$ /L
- Hemoglobin ≥ 10 g/dL
- INR $< 1.3N$ or < 3 on anticoagulants or PT ≥ 50
- Creatinine level $\leq 1.5N$
- Total bilirubin $< 1.5N$
- ASAT, ALAT $\leq 5N$
- PAL $< 5N$

In case of grade 3 or 4 non-hematological toxicity attributable to the first embolization or chemoembolization session, no further embolization or chemoembolization is performed. Only everolimus will be continued for a maximum of 24 months.

2. Everolimus dose adjustment

All toxicity will be assessed according to the NCI-CT v4.0 scale (Appendix 4).

The rules for everolimus dose adjustment in case of observed hematological and non-hematological toxicities are defined in Tables 1.1, 1.2.

All interruptions or changes to the study drug must be recorded

Monitoring of suspected everolimus toxicity

Patients whose treatment is temporarily or permanently discontinued due to an adverse event or laboratory abnormality suspected to be related to everolimus should be monitored at least weekly until the adverse event resolves or returns to grade 1. If the patient's treatment is to be delayed for more than 21 days from the day of the next scheduled dose, the patient should be excluded from the study.

Table 1.0 Guidelines for Everolimus Dose Level Changes

Dose level	Dose and frequency of administration
0 (initial dose)	10 mg per day
-1	5 mg per day
-2	5 mg every 2 days

a. **Dose adjustment for non-hematologic and hematologic toxicities**

Table 1-1 Dose adjustment criteria for everolimus toxicity and reinstatement of everolimus therapy

NON-HEMATOLOGICAL AND NON-HEPATIC Toxicity (NCI-CTC V4.0)	Actions

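### Two rows of Table 1-2 restart everolimus at 10 mg/day even when the patient had already been reduced for another toxicity

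*Protocol*

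**What the plan says.** Protocol section VII.2 sets out the everolimus dose rules. Table 1.0 labels the top level "0 (initial dose" and sets it at 10 mg per day. Level -1 is 5 mg per day and level -2 is 5 mg every 2 days.

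Tables 1-1 to 1-3 contain four first-event steps that restart treatment without a reduction:

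- Table 1-1, intolerable grade 2 non-hematological toxicity: "Then reintroduce everolimus at the same dose".
- Table 1-3, grade 3 anemia: "then resume everolimus at the same dose".
- Table 1-2, grade 2 thrombocytopenia: "Then reintroduce everolimus at the initial dose".
- Table 1-2, grade 3 neutropenia: "Then resume everolimus at the initial dose".

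Other rows impose a reduction and give no point at which it ends. For grade 3 non-hematological toxicity, Table 1-1 says "Then reintroduce everolimus at the lower dose level. For pneumonia, consider short-term steroid therapy". For grade 3 febrile neutropenia, Table 1-2 says "Then resume everolimus at the lower dose level. If febrile neutropenia recurs, discontinue everolimus". The grade 4 neutropenia row restarts one level lower and adds "If Grade 3 or 4 neutropenia occurs despite this dose reduction, discontinue everolimus".

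**The concern.** Because Table 1.0 attaches the words *initial dose* to 10 mg/day, the two Table 1-2 rows name a fixed dose. The other two first-event steps refer to whatever dose the patient was taking. The difference matters only for a patient who was reduced earlier for some other toxicity. For that patient, the earlier row put the dose at 5 mg/day or lower with no stated end, and the later row says 10 mg/day.

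One centre could return the patient to full dose immediately after a second toxicity. Another could keep the lower dose. Both could cite the protocol. At stake are the safety of that patient and consistent dosing between centres.

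**Working it through.** The plan gives no figure to reproduce on this point. The check is a comparison of the tables, a worked sequence, the dose arithmetic and a count of rules.

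**Worked sequence, using Table 1-2 only.**

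1. A patient on 10 mg/day has grade 4 neutropenia. After recovery the dose restarts one level lower, at 5 mg/day. That row's stop rule applies to neutropenia occurring despite the reduction, so it presumes the reduction is still in force.
2. The patient then has a first grade 2 thrombocytopenia. Read literally, the row restarts at 10 mg/day, the dose on which the grade 4 neutropenia occurred.
3. If the thrombocytopenia returns at grade 2, the row goes one level down, to 5 mg/day. The patient is then back on the dose held before the first thrombocytopenia.

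Under the *same dose* wording, step 2 would restart at 5 mg/day. A grade 3 reduction under Table 1-1 followed by either of the two rows gives the same conflict.

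**Dose arithmetic from Table 1.0.**

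| Level held before the interruption | Weekly dose | Literal restart | Ratio | Change |
|---|---|---|---|---|
| 0 (10 mg/day) | 10 × 7 = 70 mg | 70 mg | 70/70 = 1 | 0 |
| -1 (5 mg/day) | 5 × 7 = 35 mg | 70 mg | 70/35 = 2 | +35 mg |
| -2 (5 mg every 2 days, mean 2.5 mg/day) | 2.5 × 7 = 17.5 mg | 70 mg | 70/17.5 = 4 | +52.5 mg |

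With *same dose* the ratio is 1 in every row. Reaching level -2 normally takes two earlier one-level reductions.

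**How many rules can set up the conflict.** Rules in Tables 1-1 to 1-3 that restart at a lower level with no end point:

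- Table 1-1: grade 2 recurrence; grade 3. That is 2.
- Table 1-2: thrombocytopenia grade 2 recurrence and grade 3; neutropenia grade 3 recurrence and grade 4; febrile neutropenia grade 3. That is 5.
- Table 1-3: grade 3 recurrence. That is 1.

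The total is 2 + 5 + 1 = 8. As a *different* toxicity, 8 − 2 = 6 can precede the thrombocytopenia row. For the neutropenia row it is 8 − 3 = 5, counting febrile neutropenia as the same toxicity. The count leaves out reductions made under other parts of the protocol, such as restarts after hepatitis B reactivation (Table 2-2) or grade 3 pneumonitis (Table 1-4). It counts rules, not patients.

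**Search for a rule that settles it.** Neither document has a general statement on re-escalation, on whether reductions are permanent, or on which row governs when different toxicities follow one another. Three nearby texts each cover one situation only:

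- Table 2-2 lets a patient already on the lowest dose restart at that dose after hepatitis B reactivation.
- The strong CYP3A4 inducer rule in section VI.3 goes back to the dose taken before the inducer.
- The grade 2 row of Table 1-4 ties its reduction to recovery, which shows the protocol marks a temporary reduction when it means one.

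The SAP (section 7.6.2) only describes dose changes and compliance against 10 mg/day.

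**The case against.** The best counter-argument is that each row is a ladder for one toxicity in a patient who starts at 10 mg/day, so *initial* and *same* mean the same thing there. That is probably what the authors pictured. It is also fair that:

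- No row says a reduction is permanent. The earlier rows fix the dose at restart and do not expressly forbid a later change, so this can be called silence about sequences of toxicities.
- Within one toxicity, the severe rows already end in discontinuation: thrombocytopenia recurring after grade 3, and neutropenia after grade 4.
- The English is a rough translation, and the choice of word may come from that.
- Appendix 6, the everolimus product characteristics, is listed but its text is not in the document supplied, so it could not be checked.
- The sequence may be rare, and few investigators would double a dose just after a new toxicity. Section XIII reports under 7% grade 3-4 toxicity for everolimus, although that figure does not cover grade 2 thrombocytopenia.

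These points limit the size of the problem and leave the intended meaning open. They do not supply a rule that overrides the literal text. Table 1.0 ties the term to a specific dose, which weakens the translation argument. The grade 4 neutropenia stop rule only makes sense if the reduction continues. Rarity also has to be set against up to 24 months of exposure and a protocol list of common grade 3-4 events that includes anemia, stomatitis, thrombocytopenia and neutropenia.

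**Conclusion.** The concern holds and is minor. Two rows of Table 1-2, read as written, raise a previously reduced patient to 10 mg/day right after a further toxicity: 2 times the dose held at level -1, 4 times at level -2. Patients still on 10 mg/day are unaffected.

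The conclusion rests on reading *initial dose* as Table 1.0 defines it, and on an earlier reduction staying in force when no end point is given. The documents give no frequency for the sequence. In a single-arm trial of 72 patients the number affected could be zero or a handful. The sample size, the threshold of 31 out of 68 (SAP section 5.6.1) and the primary analysis do not depend on it.

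**What to change.** In the grade 2 thrombocytopenia and grade 3 neutropenia rows of Table 1-2, replace *the initial dose* with *the same dose (the dose level held before the interruption)*. This matches Tables 1-1 and 1-3 and changes nothing for a patient on 10 mg/day. A general rule on re-escalation is not needed.

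The cost is two phrases in one table, made by amendment or clarification letter, with no extra data, visits or patients.
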